***Follow-up:***

Patients will be informed of their results in person, or if unavailable via telephone. They will also be provided with a hard-copy report of their platelet function profiles. They will also be informed on a scheduled basis of the management plan for any serious adverse events (SAEs) that may have unfortunately occurred as a result of their direct participation in the study.

**Data Management and Statistical Analysis:**

The patient information will be initially recorded on CRFs which will be stored in the Adult Medicine Unit locking file cabinets, located at the Department of Clinical Medical Sciences, University of the West Indies, St. Augustine. Data will be coded per patient by first letter of first name, first letter of last name followed by numerical date of birth in the order of day, month, and year in a password-protected and encrypted database program in the office of Lecturer [name] at the Department of Clinical Medicine office, [name], Eric Williams Medical Sciences Complex. Each CRF and study database will be reviewed by 2 CRAs to minimize error, and clean and reconcile any conflicting data. We will aim for  $n$  of least 16 patient profiles, see sample size calculations. Any missing information will be censored and

thus, not imputed. The study biostatistician will perform routine statistical analyses with SPSS v. 11.0 software (SPSS, Chicago, IL). Continuous variables are expressed as means  $\pm$  SD. Categorical variables are to be expressed as frequencies and percentages. Student's t-test will be used to compare continuous variables. Comparisons between categorical variables will be performed using the two-tailed Fisher's exact test or Pearson's  $\chi^2$  test, as appropriate. A p-value of  $< 0.05$  will be considered statistically significant. No adjustments for multiple comparisons will be made. Results will be reported as least-square mean  $\pm$  SEM for the detailed analyses.

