Each patient will then be allocated via a computerized randomization program. Patients on DAPT for at least 6 months will be tested for platelet function testing with the P2Y12 VerifyNow assay at baseline. The patient will be administered empagliflozin 25 mg once daily for 10 days, followed thereafter by platelet function testing. The study will be randomized via a computer randomization program with a permuted block design and concealment allocation. It is also a controlled, prospective trial design, as group A serves to act as a baseline comparator group and group B has the desired antiplatelet strategy to be investigated over the longitudinal 2-week period. The study will also be blinded as patients will be unaware of their treatment assignments as well as the CRA or physician (Interventional Cardiologist) that performs the platelet function testing.

*Blood Sampling, Phlebotomy*

Blood samples for platelet function testing will be collected at baseline before the patients are administered empagliflozin (baseline sample). Blood will be drawn via an antecubital vein using a 21-gauge needle. The initial 5 mL of all blood samples will be discarded as medical waste as per the institution's policy (to avoid spontaneous platelet activation). Several laboratory tests will be performed including:

1. Complete Blood Count
2. Renal Function Profile
3. Hepatic Function Profile
4. VerifyNow P2Y12 PRU test assay - which will also be performed at the 2nd-week time point after patients have completed their assigned treatment schedules.

Overall, there will be 2 separate instances in which blood sampling/phlebotomy will be performed.

*Aggregation Testing, Platelet Function Testing*

Citrated blood samples are processed by CRAs and study investigators. The platelet function assay to be utilized is the VerifyNow P2Y12 (VN-P2Y12) assay (Accriva, San Diego, California). In brief, the VN-P2Y12 assay is a rapid whole blood point-of-care device that reports results as P2Y12 reaction units (PRU) and percent inhibition of platelet aggregation (%IPA). Assays will be performed as per the instructions of the manufacturer previously described. Please see attached:

- <http://www.accriva.com/uploads/assets/clsi-procedures/14983-revf.docx>
- <http://www.accriva.com/uploads/assets/clsi-procedures/14982-revk.doc>

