#### **Sample Size Calculation:**

Assuming:

1. A 75 mg/d clopidogrel maintenance dose required at least 5 days and a 600 mg loading dose of clopidogrel required up to 8 hours to achieve ~50% steady state of inhibition of ADP-induced platelet aggregation.
2. An estimated decrease of 10%, thus achieving a steady state inhibition of ADP-induced aggregation of 55% in patients with empagliflozin.
3. Type 1 error rate 5%
4. Statistical power of 80%

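### The statistics section aims for at least 16 patient profiles and cites a calculation whose result is n = 20 at 80% power; no stated rule links the two numbers

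*Combined protocol and SAP*

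**What the plan says.** Two sections of the combined protocol and SAP set the size of the study.

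- **Data Management and Statistical Analysis** aims for an n "of least 16 patient profiles, see sample size calculations". It does not say whether this counts patients enrolled or patients with usable results. It adds "Any missing information will be censored and" therefore not imputed. It also says that a Student's "t-test will be used to compare continuous variables", with no sidedness given; the words for two-tailed testing are attached only to Fisher's exact test.
- **Sample Size Calculation** lists four assumptions: about 50% inhibition of ADP-induced aggregation on clopidogrel; a 10% relative change, "thus achieving a steady state inhibition of ADP-induced aggregation of 55% in patients with empagliflozin"; a 5% type 1 error; and "Statistical power of 80"%. The result is n = 20, with a link to an online calculator whose address indicates a parallel-group quantitative design.

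Neither section gives a standard deviation, a loss allowance, or a label of total, per group or pairs. The Budget provides 25 sets of consent and case report forms and does not tie that count to either number.

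**The concern.** The sentence with 16 sends the reader to the sample size section for its justification, and 16 does not appear there. The number that does appear, 20, is the only one with a power figure attached. A study that closes with 16 profiles has done what the statistics section asks, and its report could then cite the 80% as though it described that study.

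The reader also cannot judge how much the gap matters in absolute terms. For a comparison of means, the sample size depends on the difference divided by the SD, and only the difference is given. If the result is not statistically significant, the planned power is of no help in interpreting it until the inputs are stated. Expected Outcomes of the Study foresees informing a Ministry of Health listing decision as well as generating hypotheses, so the size of the study should at least be stated consistently.

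**Working it through.** **Inputs from the plan.** Difference 55 - 50 = 5 percentage points; type 1 error 5%; power 80%; n = 20 (Sample Size Calculation); target of at least 16 (Data Management and Statistical Analysis). Not given: SD, sidedness, counting basis, loss allowance.

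**Step 1: try to reproduce n = 20.** For two groups, the normal approximation gives n per group = 2 × [(1.960 + 0.842) × SD / 5]², rounded up. Without an SD it has no single answer:

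| Assumed SD (points) | n per group, two-sided |
|---|---|
| 3.8 | 10 |
| 5 | 16 |
| 6 | 23 |
| 10 | 63 |

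Reading 50% and 55% as proportions of patients gives 1,565 per group, so that is not the source of 20. The plan's figure can be neither confirmed nor refuted.

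**Step 2: solve backwards.** Take the plan at its word that 20 gives 80%, and find the standardised effect d (difference / SD) that makes this true. Power is the probability that a noncentral t variable exceeds the critical t value. The noncentrality is d × √n for n pairs (n - 1 degrees of freedom), or d × √(n/2) for n per group (2n - 2 degrees of freedom). The implied SD is 5/d. All three counting bases are tried, because the methodology text describes two groups ("group A serves to act as a baseline comparator group and group B has the desired antiplatelet strategy to be investigated") and also testing before and after treatment in the same patient ("The patient will be administered empagliflozin 25 mg once daily for 10 days, followed thereafter by platelet function testing").

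**Step 3: keep that effect and reduce 20 to 16 on the same basis.** The last column is the difference detectable with 80% power at 16, at the same SD: 5 × (d needed at 16) / (d needed at 20).

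| Basis, two-sided 5% | d at 20 | Implied SD | Power at 16 | d needed at 16 | Detectable difference at 16 |
|---|---|---|---|---|---|
| Pairs: 20 to 16 | 0.660 | 7.57 | 69.5% | 0.749 | 5.67 |
| Total: 10 to 8 per group | 1.325 | 3.77 | 69.3% | 1.507 | 5.69 |
| Per group: 20 to 16 | 0.909 | 5.50 | 70.1% | 1.024 | 5.63 |

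One-sided, the effects at 20 are 0.577, 1.156 and 0.801, and the power at 16 is 71.1%, 71.0% and 71.5%.

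**Check by hand.** Under the normal approximation the SD and the counting basis cancel. Two-sided: Φ[(1.960 + 0.842) × √(16/20) - 1.960] = Φ(0.546) = 70.7%. One-sided: Φ[(1.645 + 0.842) × √(16/20) - 1.645] = Φ(0.579) = 71.9%. The loss of power is therefore nearly the same whatever the missing inputs are, provided that both numbers are counted the same way.

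**Step 4: look for a rule that would link 16 and 20.** Two would work:

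- A 20% loss: 16/0.8 = 20.
- A two-sided calculation at 20 set against a one-sided test at 16 with the same SD, which gives about 81% power at 16.

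The plan states neither.

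**The case against.** The strongest reply is that the numbers do not conflict. At least 16 is a floor, and 20 satisfies it. Follow-up uses the word profiles for test results ("They will also be provided with a hard-copy report of their platelet function profiles") and missing data are not imputed, so 16 could be the evaluable patients out of 20 enrolled. This stands as a possible reading, and it rules out saying that the figures are irreconcilable. It does not close the point: the loss allowance is not written down, and on that reading the 80% belongs to the number enrolled and not to the number analysed.

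A second reply is that this is a small study whose single objective is descriptive and whose stated uses include hypothesis generation. A non-significant result would be read mainly from its estimate and standard error, and it would not become uninterpretable because the planned power is unverified. That is fair and limits the consequence. But the plan also states a 10% effect as a hypothesis, a significance threshold and a power, and these should agree with the target.

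Three stronger readings are tempting and are not supported:

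- **That n = 20 is wrong.** Nothing shows this. Some SD makes it right on each counting basis.
- **That the plan claims 80% power for 16.** It does not say so; at most the cross-reference implies it.
- **That power at 16 could be far below 70%.** If 20 were per group and 16 a total, power would be 39.5% two-sided (45.2% one-sided) and the detectable difference 8.3 points. The reverse mix, 20 in total against 16 per group, would give 95%. No text supports counting the two numbers differently. The mixes involve 40 and 32 patients respectively, and the Budget provides 25 sets of forms. That count does not define n, but it gives these readings no help.

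The linked calculator might settle whether its output is per group or total. It could not be opened here, and its address supplies no SD.

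**Conclusion.** The point holds as an unexplained second target, together with a calculation that cannot be checked. It is not a demonstrated arithmetic error. The target that the statistics section tells the team to reach is lower than the number to which the plan attaches its power, and nothing written connects them.

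On one consistent counting basis, moving from 20 to 16 costs about 10 percentage points of power two-sided (80% to 69-70%) or 8 to 9 one-sided (80% to 71-72%). It also adds about 0.6 to 0.7 points to the detectable difference. These figures are conditional: they assume that 20 gives exactly 80%, that the SD is the same at both sizes, and that a t-test is used. They are not the trial's actual power, which is unknown without an SD.

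This should be corrected before the analysis, because the sample size is something the trial relies on and the correction is cheap. Two neighbouring matters are separate from 16 versus 20: the calculation is on percent inhibition while the null hypothesis concerns PRU, and the text describes both a between-group and a before-after comparison. They matter here only because the recalculation has to name one endpoint and one comparison.

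**What to change.** - Use one n in Data Management and Statistical Analysis and in Sample Size Calculation. Label it total, per group or pairs, and enrolled or evaluable. If 16 is meant as the evaluable number out of 20, write the loss allowance down.
- State the SD and its source (the SD of the within-patient change if the comparison is paired) and the sidedness of the t-test.
- Redo the calculation at the evaluable n for the comparison and endpoint that will be tested, and restate the power or the detectable difference.
- If 16 is kept as the target, do not present it as supported by the 80% calculation. Until an SD has been sourced, do not put another power figure in its place; the 70% above is conditional and should not be adopted as one.

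The cost is rewording and one recalculation. The stated power may be less favourable. No extra patients are needed if the power is restated. Choosing 20 evaluable means four more profiles than the floor of 16 on the same counting basis (20 - 16 = 4), or four more per group if n is per group. Holding 80% could need more, depending on the SD.

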## ***Null Hypothesis:***

There is no difference in response in patients with stable coronary artery disease on DAPT concerning PRUs on Empagliflozin.

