## **Study Design:**

The study will be a prospective, open-label study that aims to assess the effect of empagliflozin 25 mg once daily for 10 days. Patients at the Eric Williams Medical Sciences Complex (EWMSC), Mt. Hope, Trinidad and Tobago will be screened for potential eligibility.

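### Baseline PRU is collected in every patient but enters no stated comparison: the plan names only a t-test, leaves the primary contrast open, and gives no model for its least-square means

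*Combined protocol and SAP*

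**What the plan says.** The whole statement on continuous outcomes, in Data Management and Statistical Analysis, is "Student's t-test will be used to compare continuous variables". The same paragraph ends with "Results will be reported as least-square mean", plus or minus its SEM, for the detailed analyses. No model, factor or covariate is named. That section aims for an n "of least 16 patient profiles, see sample size calculations"; the Sample Size Calculation itself gives n = 20.

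Under Methodology, the VerifyNow P2Y12 assay is run before empagliflozin starts and again at the second-week "time point after patients have completed their assigned treatment schedules". Each patient therefore contributes two PRU values.

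The sections that could identify the comparison do not agree:

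- Study Design: "The study will be a prospective, open-label study that aims to assess the effect of empagliflozin 25 mg once daily for 10 days". It mentions no comparator.
- Methodology, randomisation paragraph: "group A serves to act as a baseline comparator group and group B has the desired antiplatelet strategy", in a study described as randomised and blinded.
- Null Hypothesis: "There is no difference in response in patients with stable coronary artery disease on DAPT concerning PRUs on Empagliflozin". It does not say whether the reference is the patient's own baseline or another group.
- Sample Size Calculation: the link's file name points to a parallel-group calculator for a quantitative outcome.

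**The concern.** A statistician given the locked database could defensibly run any of four analyses: a between-arm t-test on week-2 PRU, a between-arm t-test on change, ANCOVA, or a paired test within patients. They do not all answer the same question, and with 16 to 20 patients they can disagree. Nothing in the plan prevents the choice being made after the data are seen.

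There is also a question of efficiency. Baseline PRU is the obvious covariate for week-2 PRU and is already being paid for. A between-arm t-test on week-2 values ignores it. The promised least-square means do not imply adjustment, because in a two-group model without covariates they equal the arithmetic means.

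**Working it through.** **1. Is the analysis fixed anywhere?** The items needed are the contrast, pairing, the form of the outcome (week-2 value or change), baseline adjustment, and the model for the least-square means. The analysis section supplies none of them. Groups A and B and the calculator link favour a between-group contrast. The Study Design section does not, and the null hypothesis is silent. The preference is not carried into the analysis section.

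**2. The plan's own n = 20.** Stated inputs are 50% versus 55% inhibition (5 points), 5% type 1 error and 80% power. No SD is given, so 20 cannot be reproduced; only the SD it implies can be found (two-sided test assumed). With d the detectable difference in SD units:

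- 20 per arm: d = 0.909, SD = 5/0.909 = 5.50
- 20 in total, 10 per arm: d = 1.325, SD = 5/1.325 = 3.77
- 20 pairs in one group: 0.660 SDs of the change, SD of change = 5/0.660, about 7.6

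These are on the percent-inhibition scale. They carry over to PRU only if the ratio of effect to SD is the same, which the documents do not show. Step 3 therefore works in SD units and needs no SD.

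**3. Two groups: what baseline adjustment is worth.** Assumptions: bivariate normal values, equal variances, two-sided 5%, and r = 0, 0.3, 0.5 and 0.7 (not in the documents). Let m be the number per arm.

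- Post-treatment t-test: noncentrality λ = d·√(m/2), 2m − 2 degrees of freedom. Setting power at 80% gives λ = 0.909·√10 = 2.87 for m = 20, 1.325·√5 = 2.96 for m = 10, and 1.507·√4 = 3.01 for m = 8.
- ANCOVA: the residual SD shrinks by √(1 − r²), so λ becomes λ/√(1 − r²), with 2m − 3 degrees of freedom and a further small loss for chance baseline imbalance. The factor √(1 − r²) is 0.954, 0.866 and 0.714 at r = 0.3, 0.5 and 0.7. For m = 20, λ rises to 3.01, 3.32 and 4.03.

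ANCOVA power where the post-treatment t-test has 0.80 (200,000 simulated trials per cell; numerical integration over the imbalance agrees to within about 0.001):

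| Per arm | r = 0 | r = 0.3 | r = 0.5 | r = 0.7 |
|---|---|---|---|---|
| 20 | 0.789 | 0.825 | 0.891 | 0.972 |
| 10 | 0.774 | 0.810 | 0.879 | 0.965 |
| 8 | 0.766 | 0.802 | 0.871 | 0.961 |

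**4. Change-score t-test.** The SD of the change is SD·√(2(1 − r)), which is smaller than the SD of a single value only when r exceeds 0.5. With 20 per arm its power is 0.659, 0.801 and 0.951 at r = 0.3, 0.5 and 0.7, below ANCOVA each time.

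**5. Validity.** With no treatment effect, the post-treatment t-test, the change-score t-test and ANCOVA all reject in 0.049 to 0.051 of simulated trials. None inflates the type 1 error.

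**The case against.** The strongest reply is that no error has been shown. Student's t-test includes the paired form, an unadjusted two-arm t-test is valid, and the lean towards a between-group contrast is visible in the text. The gain from ANCOVA depends on an r that the documents do not give: at r = 0.3 it is 0 to 2 points, and at r = 0 it is a small loss. The harm from choosing an analysis after the data are seen is not quantified here. The stated objective is descriptive, and the expected outcomes mention hypothesis generation.

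Most of this stands, and it limits the point to an unfixed and potentially inefficient analysis. It does not remove it. A lean towards one contrast is not a specification, and another section contradicts it. The plan also sets a 0.05 significance threshold and expects its results to inform the Ministry of Health, which calls for one named comparison.

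A reader might go further and infer that an independent t-test will be run on one group's before and after values. Such a test would be conservative, with true size about 2%, 0.8% and 0.1% at r = 0.3, 0.5 and 0.7 (20 pairs). Its power loss against a paired test could be anything from under half a point (SD 3.77, 20 pairs) to about 53 points (r = 0.7, 20 pairs, SD of change about 7.6). The documents do not support that inference: no section proposes the test, and the range depends entirely on which SD is assumed. Those figures are illustrative and should not be used to size the defect.

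**Conclusion.** The point holds as an omission with a better method readily available, and it should be fixed. That the contrast, pairing, baseline use and model are unstated is clear from the text and rests on no assumption. The size is conditional. Where the post-treatment t-test has 80% power, baseline adjustment adds from almost nothing (r = 0.3) through 7 to 9 points (r = 0.5) to 16 or 17 points (r = 0.7), and costs 1 to 3 points if r is near 0. This assumes normality, equal variances, a two-sided 5% test and two randomised groups. It would be wrong to conclude that the plan specifies an invalid test or one that raises the false-positive rate.

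**What to change.** First reconcile the Study Design section with the randomisation paragraph under Methodology, so that the number of groups is settled. Then name one primary analysis of PRU:

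- **Two randomised groups:** ANCOVA of week-2 PRU on group with baseline PRU as covariate. Report the adjusted difference with its 95% CI, and take the least-square means from that model. Prefer this to a change-score t-test.
- **Single group:** mean within-patient change in PRU (week 2 minus baseline) with its 95% CI and a paired t-test. State that this cannot separate a drug effect from the passage of time or regression to the mean.

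Restate the sample-size justification for the chosen analysis on the PRU scale, with its assumed SD and, where the analysis uses it, r. The cost is a rewritten analysis paragraph and a restated calculation. Both PRU measurements are already scheduled, so no visit or blood sample is added.

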#### **Sample Size Calculation:**

Assuming:

1. A 75 mg/d clopidogrel maintenance dose required at least 5 days and a 600 mg loading dose of clopidogrel required up to 8 hours to achieve ~50% steady state of inhibition of ADP-induced platelet aggregation.
2. An estimated decrease of 10%, thus achieving a steady state inhibition of ADP-induced aggregation of 55% in patients with empagliflozin.
3. Type 1 error rate 5%
4. Statistical power of 80%

***n = 20***

([http://hedwig.mgh.harvard.edu/sample\\_size/js/js\\_parallel\\_quant.html](http://hedwig.mgh.harvard.edu/sample_size/js/js_parallel_quant.html))

#### **Quality Assurance:**

The study will be by GCP and the Declaration of Helsinki. In addition, it will only commence after official approval from the Ethics Committee of the University of the West Indies. There will be no Data Safety and Monitoring Board (DSMB). Patient Informed Consent Forms (ICFs) and Case Report Forms (CRFs) will each be quality-controlled by 2 CRAs and recorded in triplicate (1 for patient records, 2 for the study team).

#### **Expected Outcomes of the Study:**

The information obtained from the study would be integral in developing antiplatelet strategies for patients with impaired platelet reactivity. It will advance knowledge in the field i.e. useful for baseline information and hypothesis generation for further studies within the scientific community. It will also determine if empagliflozin is an adjunct for non-response to the current armamentarium of antiplatelet therapies available in Trinidad and Tobago. This information can then reliably inform regulatory bodies e.g. Ministry of Health (MOH) to make additions to the national Chronic Disease Assistance Medication Program (CDAP) to include this as a possible adjunct to facilitate a more potent antiplatelet effect.

